## 1 INTRODUCTION

### 1.1 Immunoglobulins

Since more than 5 decades immunoglobulins have been used to provide antibodies for the prevention of viral and bacterial diseases (replacement therapy) in immunocompromised patients. Within the last 30 years intravenous immunoglobulins (IGIVs) have been proven to be useful in a wide variety of clinical conditions (other than classical replacement therapy), in which IGIVs exhibit an immunomodulatory effect. These include idiopathic thrombocytopenia in children and adults at high risk of bleeding or prior to surgery to correct the platelet count, Kawasaki disease and Guillain-Barré syndrome. More recently, single IGIV brands have also been licensed for chronic inflammatory demyelinating poly(radiculo)neuropathy and multifocal motor neuropathy. Experimental off-label use of IGIV in other neurological and dermatological indications is widespread.

However, immunoglobulins may also be administered by subcutaneous (SC) infusion. The administration via the SC route offers several advantages over IV infusion from a patient's and a physician's perspective. After the introduction of small, portable syringe drivers, this route of administration has gained even more popularity in several European countries and in the US as a practical, effective, and safe administration of treatment. In addition, home therapy can also be recommended with SC administration. An administration at home with small portable pumps can easily be learned by the patients or their caregivers. It may remarkably improve the patient's quality of life and compliance as it reduces the frequency of hospitalizations and the need for home care. Administration of IgG via the SC route provides more stable and well-balanced IgG plasma levels until the end of the treatment interval, in contrast with the peak IgG plasma concentrations attained with IGIV, which weaken at the end of dose. When effective IGIV therapy cannot be continued because of the lack of peripheral and central vein access, SC immunoglobulins (SCIG) might also be an alternative treatment option.

*octanorm*, the investigational medicinal product (IMP) in this study, is an immunoglobulin preparation from human normal plasma and is manufactured by Octapharma. It contains 16.5% (165 mg/mL) protein. The product is aimed for SC infusion by pump or syringe.

Further information on the IMP can be found in the Investigator's Brochure.

### 1.2 Idiopathic Inflammatory Myopathies

Idiopathic inflammatory myopathies (IIMs) are a heterogeneous group of acquired, systemic connective tissue diseases characterized by chronic inflammation of striated muscles leading to predominantly proximal muscle weakness. They are best classified on the basis of their varying clinical characteristics into the most common subsets of IIM: adult dermatomyositis (DM) and polymyositis (PM), juvenile DM, necrotizing autoimmune myositis, myositis in overlap with cancer or another connective tissue disease, and inclusion body myositis. IIMs are frequently associated with constitutional symptoms and commonly involve other organ systems including the skin, joints, lungs, gastrointestinal tract and heart. Patients with IIM have increasing difficulty with tasks requiring the use of proximal muscles, such as getting up from a chair, climbing steps, or lifting objects. In rare acute cases also respiratory muscles can be affected. Extra-muscular disease activity may manifest in systemic symptoms like fever, arthralgia, and Raynaud's phenomenon, cardiac arrhythmias or ventricular

dysfunction, and pulmonary complications, primarily due to interstitial lung disease (reported in 10-40% of patients).

IIMs are rare with an estimated incidence of 4-10 cases/million population per year, and a bimodal incidence pattern reflecting childhood onset of juvenile DM and a later peak in adulthood.

Each IIM subtype has a different prognosis and response to therapies so that the distinction from other diseases is very important. Although the precise pathogenesis is unknown, the IIMs likely result from immune-mediated processes initiated by environmental factors in genetically susceptible individuals.

Although a spectrum of severity exists for DM, this entity is more likely to be associated with rapid and aggressive myositis. DM is seen in both, children and adults, and the early symptoms include distinct skin manifestations accompanying or preceding muscle weakness. The classic skin manifestations include periorbital heliotrope (blue-purple) rash with edema; erythematous rash on the face, knees, elbows, malleoli, neck, anterior chest (in a V-sign), and back and shoulders (in a shawl sign); and a violaceous eruption (Gottron's rash) on the knuckles, which may evolve into a scaling discoloredation. The lesions are photosensitive and may be aggravated by ultraviolet radiation.

The risk of cancer is increased in adults during the first 3-5 years after the onset of DM, with a reported frequency of 9-32%; necessitating a thorough annual workup in the first 3 years after disease onset. The most common forms are ovarian, breast, and colon cancer, melanoma, and non-Hodgkin's lymphoma.

### 1.3 Rationale for Conducting the Study

During the last 20 years, several IgG preparations have been developed for intravenous (IV) and subcutaneous (SC) administration, and their use has further contributed to the successful treatment of patients requiring replacement therapy.

In addition to its use for the treatment of primary and secondary immunodeficiencies, IGIV is increasingly used for immunomodulating therapy in the treatment of patients with a variety of autoimmune and inflammatory neurological disorders. One placebo-controlled clinical study in 15 subjects with refractory DM employed a dose of 2.0 g/kg IGIV or placebo for 12 weeks. After a 1-month washout phase the subjects crossed over to the alternate therapy. Subjects on IGIV had a significant improvement in muscle strength and neuromuscular symptoms in contrast to subjects on placebo. A total of 12 subjects received IGIV of which 9 subjects had a major improvement to nearly normal function.

Currently, Octapharma is conducting the study ProDERM: “**Progress in DERMatomyositis**” (study number GAM10-08) to investigate efficacy, safety and tolerability of the IGIV Octagam 10% in DM patients and to confirm the efficacy results, which were observed in the small randomized placebo-controlled cross-over trial  and also seen in retrospective studies or case reports, in a much larger setting. Furthermore, ProDERM will systematically investigate the long-term beneficial effect of IGIV in a 6-month open-label extension period. Long-term safety and tolerability of high-dose Octagam 10% (2.0 g/kg) administered for up to 40 weeks will be investigated, since many patients need lifelong treatment. Eventually, Octagam 10% should offer DM patients an additional effective and safe maintenance treatment option that is well tolerated.

The rationale for conducting this study (SubQ-DERM: “Progress with **Subcutaneous** Immunoglobulin in **DERM**atomyositis) is to determine the efficacy of the SCIG *octanorm* administered subcutaneously for 32 weeks compared with placebo in the maintenance treatment of patients with DM who have previously responded to IGIV therapy and to assess treatment outcome, effect on Quality of Life (QoL) measures, compliance and safety of treatment with *octanorm*.

The administration of immunoglobulins via the SC route offers several advantages over IV infusion from a patient’s and a physician’s perspective. Replacement therapy by rapid SC infusion with a pump was introduced during the late 1980s. Several reports have shown that the SC method is feasible, safe, efficient, cost-effective and highly appreciated by the patients.[5-13]

#### 1.4 Dose Rationale

Findings from the animal experiments performed with *octanorm* (efficacy, safety pharmacology and local tolerance) in different species (mice, rabbits, and dogs) justify the safe use of *octanorm* in humans. No animal pharmacokinetic studies were performed with *octanorm* because pharmacokinetic parameters in animals treated with human immunoglobulin solutions cannot be extrapolated into humans.

There are two major differences in the PK characteristics of IGIV and SCIG: delayed absorption and reduced bioavailability.

Following IV administration, the plasma concentration peaks immediately upon termination of the infusion. After SC administration, the absorption of IgG into the subcutaneous tissue is slower; the IgG must be delivered into the bloodstream by the lymphatic system. Thus, with SCIG, the intravascular IgG concentration increases gradually, peaking at 48–72 hours. In three recent studies comparing IGIV and SCIG in PID patients, the mean peak serum IgG level immediately after IV infusions was 2303 mg/dL.[12, 14, 15] In contrast, the mean peak with SCIG was 1410 mg/dL.[16]

No differences have been reported in the half-life of SCIG and IGIV. With modern IgG preparations, half-lives have generally been reported to be about 30–35 days.[17]

The use of smaller doses of SCIG at more frequent intervals result in stable, higher trough IgG serum concentrations, which remain constant between consecutive SCIG infusions.[18]

Pooled data from 7 studies in which equivalent monthly SC IgG doses were given weekly vs. IGIV every 21–28 days showed that trough serum IgG levels were 10 to 20% higher with weekly SC doses than with the same total monthly IGIV dose. After 6 to 12 weekly infusions, near-steady-state IgG levels were achieved with differences between minimum and peak concentrations of only 5% to 10% of the overall mean.[16, 17]

Thus, on converting from IGIV to SCIG replacement therapy, the equivalent monthly dose of IgG is usually determined in one of two ways:

- 1:1 dosing: The 3 to 4 weekly IGIV dose is split into 3 to 4 equal weekly SCIG infusions.
- Dosing based on the area under the curve. The SCIG dose is calculated from PK data to provide a monthly exposure to IgG equivalent to that with IGIV.

The former is common in Europe, while the latter is a requirement of the US Food and Drug Administration (FDA) for SCIG labeling studies in patients with primary antibody deficiency.[19]

In an open label study in seven female patients (4 with DM, 3 with PM) SCIG was administered at the patients' usual IGIV monthly dose fractioned into equal doses given subcutaneously at weekly intervals. The median follow-up period was 14.4 months. During the treatment period, no relapse of disease occurred. All patients showed a good clinical response and reported good tolerance to the treatment with an improved quality of life.[20]

Therefore, the dose of 0.5 g/kg BW given on a weekly basis proposed for this study a 1:1 equivalent to the IGIV of 2 g/kg BW given every 4 weeks used in the GAM10-08 study, and thus is considered appropriate to determine the efficacy of *octanorm* for the maintenance therapy of patients with DM.

With weekly SCIG administrations, only about 4.4 days elapse between the  $t_{max}$  of one dose and the administration of the next dose. Given the half-life of 30 days this means that only about 10 to 20% of the administered IgG is metabolized before the serum level starts to rise again. In contrast, with IGIV dosing intervals of 3–4 weeks (about one half-life), 36 to 48% of the IgG may be metabolized by the time the next dose is due. These differences in the dosing intervals used in most SCIG vs. IGIV regimens result in more stable serum IgG levels with SCIG.[16, 17]

## 1.5 Benefit-Risk Statement

Despite its well-established safety profile, IGIV often leads to undesired symptoms, ranging from mild systemic adverse reactions, such as flushing, fever, muscle aches, tiredness, headache and dizziness, to severe reactions, manifesting as chest pain, tachycardia, and changes in blood pressure, aseptic meningitis, thrombosis or renal failure.[18]

The slower rate of rise towards the peak and the truncation of its height are believed to be responsible for the much lower incidence of systemic adverse events (AEs) with SCIG. This is consistent with observations that many AEs of IGIV infusions are rate-related, and has been repeatedly confirmed.[21]

On the other hand local reactions at SC injection sites are common. These reactions are rarely severe, and are accepted by most patients. In the meta-analysis by Orange et al. the reporting rate varied from 0.028 to 0.697 per infusion demonstrating that the majority of patients tolerate SCIG well.[19]

Subjects with pre-existing risk factors for thrombotic events (such as advanced age, obesity, hypertension, diabetes mellitus and a history of vascular disease or thrombotic episodes, subjects with acquired or inherited thrombophilic disorders, subjects with prolonged periods of immobilization, severely hypovolemic subjects, subjects with diseases which increase blood viscosity) may be at risk.

Subjects with DM may be at higher risk of developing thromboembolic events (TEEs). Therefore, special emphasis will be given to the occurrence of TEEs such as deep vein thromboses (DVTs) and pulmonary embolism (PE).

Hemolytic transfusion reactions (HTRs) can develop subsequent to IgG therapy. IgG-related hemolysis is associated with passive transfer of anti-A and anti-B hemagglutinins.

When medicinal products prepared from human blood or plasma are given to a subject, the transmission of infectious agents cannot be totally excluded. This applies also to hitherto unknown pathogens. However, specific virus inactivation procedures are implemented in the manufacturing process of *octanorm*, which are described in detail in the Investigator's Brochure.

The safety profile of SCIG is well characterized. For *octanorm*, the same type of adverse reactions may be expected. No new or unknown safety problems are expected to emerge for *octanorm*, which are not already described in the Investigator's Brochure.

As per European Federation of Neurological Societies (EFNS) Guidelines [22], IGIV is recommended as a second-line treatment in combination with prednisone in DM (level B) and treatment option in PM (level C). This is in line with the consensus statement of the American Association of Neuromuscular and Electrodagnostic Medicine (AANEM) ad hoc committee on the use of IGIV in the treatment of neuromuscular conditions: Class I evidence exists to support the use of IGIV to treat patients with DM.[23] Over the last years, high-dose IGIV has become an effective and safe therapeutic option for DM and is beneficial as a second-line therapy for DM.[24] The European Dermatology Forum stated in their "Guideline on the use of high-dose intravenous immunoglobulin in dermatology" that, besides Pemphigus vulgaris, DM is the dermatological condition with the highest level of evidence for treatment with IGIV.[25] IGIV is indicated for all severe forms of DM and its use as first-line treatment may be justified in patients with fulminant progressive courses, severe myolysis or paralysis. As a rule, IGIV should be used as a second-line treatment if steroid monotherapy has failed to produce an improvement after 1 month, or if reducing the steroid dose below an acceptable level results in a flare-up of the disease, or if side-effects prevent further steroid medication. The use of IGIV therapy is considered to be an adjuvant treatment with continuation of immunosuppressive therapy with corticosteroids and possibly also other immunosuppressive agents.[25, 26] The German Society for Neurology also recommended in their Guideline to treat patients who do not respond to corticosteroids, azathioprine or methotrexate with IGIV (Class I evidence). Similarly, the Guideline of the Therapeutics and Technology Assessment Subcommittee of the American Academy of Neurology concluded that based on one Class II study, IGIV is possibly effective for the treatment of nonresponsive DM in adults and thus may be considered for the treatment of nonresponsive DM in adults (Level C).[4, 27]

Because of the ease of its application, IGIV has become the treatment of choice as corticosteroid-saving agent or as add-on therapy in severe myositis.[28]

Immunoglobulins administered via the SC route are likely to show the same efficacy as those administered by IV route.

In terms of therapeutic benefits, it can reasonably be assumed that *octanorm* will exhibit the same efficacy, safety and effectiveness as other SCIG brands.

---

 Leitlinien für Diagnostik und Therapie in der Neurologie – Myositissyndrome;  
[www.dgn.org/leitlinien/3011-ll-69-ll-myositis-syndrome](http://www.dgn.org/leitlinien/3011-ll-69-ll-myositis-syndrome)

## **2 STUDY OBJECTIVES**

### **2.1 Primary Objective(s)**

The primary objective of this study is to determine the efficacy of subcutaneous immunoglobulin *octanorm* in the maintenance treatment of DM patients who have previously responded to IGIV therapy.

### **2.2 Secondary Objective(s)**

The secondary objectives of this study are:

- to assess other efficacy outcomes at the end of study (Week 32 or Drop-Out Visit)
- to assess the effect of *octanorm* on Quality of Life (QoL) measures;
- to assess the treatment compliance of home treatment with *octanorm*;
- to evaluate the safety and tolerability of *octanorm* in subjects with DM.

Property of Octapharma. Do not copy or distribute without written permission.

### 3 INVESTIGATIONAL PLAN

#### 3.1 Primary and Secondary Endpoints

##### 3.1.1 Primary Endpoint(s)

- Proportion of patients with clinically important deterioration in the treatment period. A patient with clinically important deterioration is defined as a patient with 1) MMT-8 worsening  $\geq 6$  points (scale of 150) OR CDASI (Total Activity Score) worsening  $\geq 5$  points, AND 2) a Physician's Global Disease Activity VAS worsening  $\geq 2$  cm.

##### 3.1.2 Secondary Endpoint(s)

###### Efficacy:

- Mean change from Baseline (Week 0-defined as end of IGIV therapy) to end of the treatment period (Week 32 or Drop-Out Visit) in:
  - Modified Cutaneous Dermatomyositis Disease Area and Severity Index (CDASI);
  - Six Myositis CSM (MMT-8, Physician's Global Disease Activity, Patient's Global Disease Activity, Extra-Muscular Disease Activity, Muscle enzymes, Health Assessment Questionnaire (HAQ);
  - SF-36v2 Health Survey.
- Mean change in TIS from Baseline (Week 0) to end of treatment period (Week 32 or Drop-Out Visit).
- Time to clinically important deterioration during the treatment period.
- Number and type of deviations from protocol requirements relating to home treatment (dosing, timing).

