#### 3.2 Overall Study Design and Plan

This study is planned to start in Q3 2018 and to be completed by Q2 2020, resulting in an overall duration of 24 months.

It will be a double-blind, randomized, placebo-controlled, parallel group, multicenter, comparative efficacy and safety study in a minimum of 78 adult subjects of both genders with

[figure not shown]
definite or probable DM according to the criteria of Bohan and Peter [29, 30] who have previously responded to IGIV therapy.

As DM is a rare disease, about 45 sites are projected to participate in countries worldwide with emphasis on European countries and North America.

Subjects eligible after screening will be randomized 1:1 to receiving up to 32 infusion cycles of either *octanorm* 0.5 g/kg/week or placebo every week for 32 weeks. The weekly infusion will be performed in two separate sessions (= 1 infusion cycle for a given weekly administration). An infusion cycle comprises both sessions to be administered on 1 or 2 days, either on the same day or on two consecutive days or with maximum one day in between two sessions.

In case of clinically important deterioration (for definition see Section 4.3.1) during the SC treatment period, subjects will be discontinued from the study, will undergo a termination visit and may optionally receive Octagam 10% as IGIV rescue medication (2g/kg BW one time, provided by the sponsor) or rescue treatment according to standard of care at the site by the treating physician. Octagam 10% or any other commercially available IGIV as optional IGIV rescue medication can be also reimbursed by the sponsor (2g/kg BW one time). IGIV as rescue medication should be administered with infusion rate not higher than 0.04 mL/kg/min (240 mg/kg/h).

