### 4.3 Withdrawal and Replacement of Subjects/Patients

#### 4.3.1 Premature Subject/Patient Withdrawal

Subjects have the right to withdraw from the study at any time for any reason, without the need to justify their decision. The Investigator also has the right to withdraw subjects in case of AEs, poor compliance, or other reasons. Since an excessive rate of withdrawals can render the study non-interpretable, any unnecessary withdrawal by investigator's decision should be avoided.

For any withdrawals after study entry, the Investigator will obtain all the required details and document the reason(s) for discontinuation. If the reason for withdrawal of a subject/patient is an AE, the main specific event or laboratory test will be recorded, and the Investigator will make thorough efforts to clearly document the outcome.

Should a subject decide to withdraw, the Investigator will make the best efforts to complete and report the observations. The Investigator will document the reason(s) for withdrawal of each subject in the eCRF.

Subjects who terminate the study prematurely are drop-outs. The Investigator has to organize the Drop-out visit which is identical to the Termination visit procedures.

Other reasons for premature termination of subjects may be:

1. Withdrawal of subject's consent.
2. Deterioration of DM.
3. Pregnant subjects will be immediately excluded from the study.
4. Investigator's opinion that the subject may be severely harmed if he/she continues trial participation, namely by the treatment and procedures according to the study protocol.
5. Occurrence of a disease which interferes with the study treatment or represents an exclusion criterion.
6. Administration of IgG other than *octanorm*.

"Clinically important deterioration" is defined as follows:

- 1) MMT-8 worsening  $\geq 6$  points (scale of 150) OR CDASI (Total Activity Score) worsening  $\geq 5$  points,  
AND
- 2) Physician's Global Disease Activity VAS worsening  $\geq 2$  cm.

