In case of clinically important deterioration during the treatment period, subjects will be discontinued from the study, will undergo a termination visit and may optionally receive Octagam 10% as IGIV rescue medication (2g/kg BW one time, provided by the sponsor) or rescue treatment according to standard of care at the site by the treating physician. Octagam 10% or any other commercially available IGIV as optional IGIV rescue medication can be also reimbursed by the sponsor (2g/kg BW one time). IGIV as rescue medication should be administered with infusion rate not higher than 0.04 mL/kg/min (240 mg/kg/h).

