### 9.1 Determination of Sample Size

The sample size calculation is based on the target parameter for the evaluation of the primary endpoint, i.e. the proportions of patients with clinically important deterioration in the active treatment arm (*octanorm*, 0.5 g/kg/week) and the Placebo arm until the end of the 32 week treatment period.

Patients who drop out prematurely or receive rescue treatment for any safety reason or lack of efficacy will also be analysed as patients with clinically important deterioration.

The following assumptions for the true proportion of patients to be analysed as patients with clinically important deterioration, which will include all dropouts, were chosen for the sample size calculation after thorough discussion with Steering Committee members involved in the treatment of DM patients:

- Octanorm arm: 27% (this corresponds to a failure rate of 18.89% in patients randomised to octanorm who completed the study per protocol plus a 10% drop-out rate)
- Placebo arm: 58% (this corresponds to a failure rate of 53.33% in patients randomised to Placebo who completed the study per protocol plus a 10% drop-out rate)

The pair of hypotheses to be tested is:  $H_0: P_O = P_P$  vs.  $H_A: P_O \neq P_P$

where  $P_O$  and  $P_P$  denote the proportions of patients with clinically important deterioration in the *octanorm* and Placebo arm respectively.

With these assumptions, a sample size of 39 patients per treatment arm will be needed to achieve a power of 80% to detect a difference between the group proportions, using the Pearson Chi-square Test for Proportion Difference at a significance level of  $\alpha=0.05$ . It is therefore planned to enrol a minimum of 78 patients, randomized to the two treatments groups in a balanced 1:1 ratio.

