## **9.10 Handling of Missing Data**

For missing data with respect to the primary endpoint evaluation, please refer to Section 9.7.1.

For missing weight measurements the last available body weight will be used for all calculations related to dosing; in individual patient data listings such last observations carried forward (LOCF) will be tagged.

Missing data in other variables caused by subjects who dropped out of the study or for other reasons will not be replaced by any methods of imputation. Instead, frequency of missing values will be presented.

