10.2. Secondary efficacy endpoints

All secondary efficacy endpoints will be analyzed and presented in full detail by means of descriptive statistics and inferential analyses as appropriate.

For CDASI, SF-36v2, TIS, and the individual CSMs the mean change from Baseline (Week 0) to the end of treatment will be presented by a full set of descriptive parameters: number of subjects with non-missing values, mean, standard deviation, median, minimum and maximum, 1st and 3rd quartile, 95% CI.

Moreover, for those continuous secondary endpoints, an analysis of covariance (ANCOVA) will be used to analyze changes from baseline to end of treatment (Week 32 or earlier end of treatment visit). The model will include treatment as a fixed factor. Center will be included as random factor. The baseline value of the variable to be analyzed will be included as a covariate. Least square means will be derived and presented together with 95%-confidence intervals by treatment group. Moreover, two-sided 95% confidence intervals will be derived for the overall difference in least square means between Octanorm and placebo treatment.

The time to clinically important deterioration will be analyzed by the product-limit method for the analysis of survival data, and presented as Kaplan-Meir plots alongside a Log-Rank test for differences between treatment groups.

The detailed list of all tables, figures and graphs, and the analysis populations used for each analysis will be provided in a separate document later, when all feedback from authorities will be available.

Property of Octapharma. Do not copy or distribute without written permission.

11. Safety and Tolerability Analyses

The safety analysis will comprise descriptive statistics, tabulations and listings of all treatment emergent adverse events (TEAEs), safety laboratory results, viral markers, vital signs, Wells' scores, Doppler scan results, and physical examination findings.

The safety analysis will be made with the SAF population. Patients will be analyzed by actual treatment, data tabulations will present the treatment arms and the total count in a side-by-side manner.

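### The mean-change secondary endpoints compare the arms at last on-study assessment, on average about 3 to 6 weeks earlier on placebo, and no by-visit analysis is specified

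*Protocol*

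**What the plan says.** - **Endpoint.** Protocol 3.1.2 defines change in CDASI, the six core set measures (CSM) and SF-36v2 from baseline "to end of the treatment period (Week 32 or Drop-Out Visit". TIS has the same timing. The secondary objective in Protocol 2.2 uses it too, so the timing is declared.
- **Analysis.** SAP 10.2 fits an ANCOVA to "changes from baseline to end of treatment (Week 32 or earlier end of treatment visit", with treatment fixed, center random and baseline as covariate. It specifies no repeated-measures model and no term for the time of assessment.
- **Removal.** After clinically important deterioration, "subjects will be discontinued from the study, will undergo a termination visit" (Protocol 3.2; likewise 4.3.1). The definition is MMT-8 worsening of at least 6 points or CDASI worsening of at least 5 points, together with Physician's Global VAS worsening of at least 2 cm. For other early exits, "The Investigator has to organize the Drop-out visit which is identical to the Termination visit procedures".
- **Expected exits.** Protocol 9.1 gives "Placebo arm: 58% (this corresponds to a failure rate of 53.33"% among completers plus 10% drop-out. The octanorm figure is 27%, from 18.89% plus 10%.
- **Data available.** CSM and CDASI are assessed every 4 weeks from Week 4 to Week 32. SF-36v2 is assessed at baseline and termination only.
- **Status.** Protocol 9.4 makes every test other than the primary one exploratory. SAP 8.3 rules out analysing patterns of missing data.

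**The concern.** One value per patient is compared between arms, but when that value is taken depends on how the patient did. More placebo patients are expected to leave, so their values come from earlier in the study on average. Three of the measures analysed also enter the rule that sends patients out: MMT-8, CDASI and the Physician's Global VAS. At exit, those values are partly selected for being poor.

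At stake is what the least-squares mean difference means. SAP 2 foresees use in regulatory submissions and manuscripts, where a result labelled end of treatment in a 32-week trial is easily read as a Week-32 effect. It would not be a difference at any common time. The values collected at Weeks 4 to 28 in patients who continue, which could give a same-time comparison, are not used in the specified model.

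**Working it through.** **1. The plan's own figures.** Rates (Protocol 9.1): placebo 0.9 × 0.5333 + 0.10 = 0.580; octanorm 0.9 × 0.1889 + 0.10 = 0.270. Sample size with pooled variance, two-sided 0.05 and 80% power: n = [1.960 × √(2 × 0.425 × 0.575) + 0.842 × √(0.58 × 0.42 + 0.27 × 0.73)]² / 0.31² = 38.7, so 39 per arm. The stated figure is reproduced.

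**2. Who supplies an exit value.** Deterioration accounts for 0.9 × 53.33% = 48% of placebo and 0.9 × 18.89% = 17% of octanorm patients, plus 10% other drop-outs per arm. That is up to 0.58 × 39 = 22.6 against 0.27 × 39 = 10.5 patients, some of whom exit at Week 32 itself.

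**3. Mean week of assessment.** The documents give no exit times, so four patterns over the eight 4-weekly visits were assumed, with every exit yielding a value.

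Constant rate: the per-interval retention is s = (1 − p)^(1/8), which is 0.897 (placebo) and 0.961 (octanorm). Mean week = 4p/(1 − s): 4 × 0.58/0.1028 = 22.6 and 4 × 0.27/0.0386 = 28.0. Share assessed at Week 32 = (1 − p)^(7/8): 46.8% and 75.9%.

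For the other three patterns the distribution of exit weeks is the same in both arms, so the gap = (0.58 − 0.27) × (32 − mean exit week).

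| Pattern | Placebo | Octanorm | Gap (weeks) | Before Week 32, placebo / octanorm |
|---|---|---|---|---|
| Constant rate | 22.6 | 28.0 | 5.4 | 53% / 24% |
| Uniform (mean exit week 18.0) | 23.9 | 28.2 | 4.3 | 51% / 24% |
| Early (12.2) | 20.5 | 26.7 | 6.1 | 55% / 26% |
| Late (23.0) | 26.8 | 29.6 | 2.8 | 44% / 20% |

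The 6.1 is 0.31 × 19.8; subtracting the rounded means gives 6.2. As a share of a linear 32-week drift common to both arms: 2.8/32 = 9% to 6.1/32 = 19% (constant rate 5.4/32 = 17%).

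**4. Net effect on the difference.** This needs disease courses that the documents do not give, so the following are illustrations.

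- *MMT-8.* Assumed: linear worsening, mean 8 against 1 points by Week 32; between-patient SD 4 to 8; measurement SD 1 to 3 points and 0.4 to 1.0 cm on the VAS; VAS tracking MMT-8 at 0.35 cm per point. The Week-32 difference of 7.0 becomes 4.6 to 5.9 at Week 32 or exit. The three scenarios nearest the planning rates give 4.6 to 5.2. The standardised difference falls by only about 5% to 9%. Recorded exit values of deteriorators are 0.4 to 4.6 points worse than their underlying state, which is the selection effect. With identical arms the difference is 0.0.
- *CDASI, progressive worsening* (0.5, 0.7 or 1.2 points per week): last-visit difference 2.8 to 3.5 against 4.6 to 9.7 at Week 32.
- *CDASI, fluctuating* (autocorrelation 0.6, SD 3.5, arm shift 2.4): 3.4 against 2.4, about 40% too large. If the exit value is taken two weeks after the trigger, the excess falls to about 29% (VAS correlation assumed).

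**5. What a repeated-measures model recovers in the CDASI cases.** It gives 3.6 to 3.7 where Week 32 is 4.6 to 5.9, 3.5 where it is 9.7, and 2.4 where it is 2.4. The simulated SD of the difference is 1.1 to 1.6 points, against 0.8 to 0.9 for the last-visit difference.

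**The case against.** The strongest reply is that the plan openly names its target. Protocol 2.2 and 3.1.2 and SAP 3.2.2 and 10.2 all state Week 32 or the earlier exit, and none calls the result a Week-32 difference. Status at exit is a legitimate target. These analyses are exploratory, time to deterioration has its own Kaplan-Meier and log-rank analysis, and SAP 8 promises descriptive statistics for all data. The table list is still to come, so by-visit summaries may yet appear. All of this stands. It makes the point one of labelling and a supplementary analysis. It does not supply a same-time comparison, because no by-visit model is specified.

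Four stronger readings are tempting, and the documents do not support them:

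- *A conflict with Protocol 9.10*, under which missing values "will not be replaced by any methods of imputation". There is none: the drop-out value is the defined endpoint value, so it is observed and not imputed.
- *That every endpoint rests on values selected for being bad.* Direct selection reaches at most three measures, and since the rule says MMT-8 or CDASI, only one of those two need be extreme. The others are affected only through timing and correlation. TIS does not separate stable from worsening patients (Protocol 7.2.2), and the 10% who leave for other reasons are not selected by the deterioration rule.
- *That the exit value is the triggering value.* The text says only that a termination visit follows.
- *That the comparison is biased in a known direction or produces false positives.* Direction depends on disease course, and identical arms give no difference. A spurious difference from common drift requires a measure unaffected by treatment while exits differ by arm.

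**Conclusion.** The point holds as one of interpretation. The planned difference is a difference at last on-study assessment, with placebo assessed 2.8 to 6.1 weeks earlier on average. That rests on the plan's 58% and 27%, on the four assumed exit patterns, and on every exit yielding a value. The further consequence is uncertain in size and sign: smaller than the Week-32 difference in the progressive scenarios, larger in the fluctuating one, all under assumed trajectories. The primary endpoint does not use these means, so its conclusion is unaffected. The change is worth making because the by-visit data will already exist and the cost is analysis work alone.

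**What to change.** In SAP 10.2:

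1. Keep the ANCOVA, label its result *change to last on-study assessment*, and tabulate the week of that assessment by arm.
2. For measures taken at every visit (CDASI, MMT-8, the three VAS, HAQ, enzymes), add a supplementary MMRM on all values up to discontinuation and before any rescue. Include treatment, visit, treatment-by-visit, baseline and baseline-by-visit, and report differences at each visit and at Week 32.
3. Give a rule mapping off-schedule drop-out visits to scheduled visits, including which value counts if two fall in one window. Name a fallback covariance structure: an unstructured one over eight visits has 8 × 9/2 = 36 parameters, and under a constant exit rate only about 0.468 × 39 = 18 placebo patients are assessed at Week 32.
4. State that the Week-32 contrast is a hypothetical estimate, as if nobody were removed, under missing-at-random. That is plausible for removal triggered by recorded scores and less certain for other drop-outs. State also that it is less precise than the ANCOVA and may still understate fast progression.

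SF-36v2 (two time points) and TIS (does not register worsening) lie outside item 2. The cost is SAP wording and one model per measure. It can be done before unblinding, since SAP 4.3 places finalisation of the SAP before that step and the table list is still open.
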